A recent study (C-SURFER) evaluated the safety and efficacy of 12 weeks of grazoprevir and elbasvir for HCV genotype 1 patients with CKD stages 4/5. The study was designed to randomize eligible patients to either immediate or deferred treatment with grazoprevir and elbasvir. The delayed treatment arm received placebo and was treated with grazoprevir and elbasvir subsequently. The study participants were HCV genotype 1, CKD stages 4/5 (eGFR <30), and 76% were on hemodialysis, and 46% were African Americans. A small number of patients with compensated cirrhosis were allowed. The study reported an intention to treat (ITT) and modified ITT analysis of 94% and 99% for SVR12. There were no changes in hemoglobin or other adverse events or erythropoietin use in the immediate treatment group compared to placebo. Four percent of patients in the deferred treatment group discontinued treatment due to an adverse event, mainly headache, nausea or fatigue (17). In summary, a regimen of grazoprevir and elbasvir could be an effective regimen to treat HCV genotype 1 infection in patients with severely compromised renal function.

While studies evaluating the safety and efficacy of this regimen in patients with chronic kidney disease have shown success with few adverse events, little is known about the efficacy of this, or any other, therapy in patients on immunosuppression after renal transplantation or whether it is optimal to treat hepatitis c before or after transplantation. Because waiting until after transplant to treat patients for HCV is advantageous by allowing those patients to receive HCV-positive donor organs, most centers are waiting to treat these patients. In order to observe whether there is any difference immunologically or clinically in treating patients before or after renal transplantation, we will compare our transplant cohort to a cohort of historical, non-transplant patients treated for HCV in whom we have stored blood samples from prior IRB-approved studies.

Significance

The prevalence of chronic hepatitis C in patients with CKD is much higher than that observed in the general population (18). This highlights the importance of finding a ribavirin free regimen that is not excreted through the kidneys. However, it is unclear what the timing of HCV therapy should be for these patients.

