
2.7 Statistical Analysis and Sample Size Justification
	
Data analysis will be completed by the study biostatistician.
 
Primary Endpoints
 
Primary Objective 1. The primary endpoint for this objective will be the measurement of host immune responses using ISG expression including IP-10 levels, and HCV specific T-cell responses. ISG expression and IP-10 levels will be measured before and 4 weeks after completion of therapy. HCV specific T-cell responses will be measured before and during SVR 12 (12 weeks after completion of the study medications).
 
Primary Objective 2. The primary endpoint for this objective will be the measurement of SVR 12. This will be measured at study week 24/28, or 12 weeks after completion of the study medications.
 
Secondary Endpoints
 
Secondary Objective 1. We will assess the safety of the medications using adverse event monitoring. The primary endpoint for this objective will be the presence of any severe adverse event. A secondary endpoint will be the early discontinuation of the study medications. This will be assessed at the study visits weeks 0, 4, 8, and 12. Based upon prior trials with these investigational drugs, we estimate rate of serious adverse events of about 15% (17).
 
Secondary Objective 2. The primary endpoint for this objective will be episodes of rejection and graft survival for post-transplant patients after treatment and will be recorded via medical record abstraction as part of their enrollment in the ongoing prospective cohort study to assess treatment efficacy in chronic hepatitis C (HP – 00063362).
 
Research data will be collected and managed using REDCap (Research Electronic Data Capture) hosted at the University of Maryland, which is a secure, web-based application to support data capture for research studies. All of these variables will be entered into REDCap by study staff at the end of each study visit based upon the labs obtained, patient questionnaires, and interim records reviews, and after the initial 30 to 34 weeks of the study based upon medical records reviews.
 
Statistical Methods
 
Clinical treatment arm
 
All statistical analyses will be based on an intention-to-treat model, including all enrolled patients who received at least one dose of study medication. Both the primary efficacy and safety endpoints will be based on the proportion of patients with SVR 12 and severe adverse events, respectively, with point estimates and 95% confidence interval. Both primary efficacy and safety endpoints will be compared to a non-transplant, HCV-infected historical control group by using two-sided, exact one-sample binomial test at a significance level of 0.05. Demographic and baseline characteristics will be summarized using standard descriptive statistics overall and by patient cohort. Univariate logistic regression will be performed to identify baseline factors associated with SVR 12 at a significance level of 0.05.
 
Measurement of host immune response

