
	
Mann-Whitney or Wilcoxon matched-pairs signed rank test will be used for 2-group comparisons, and a linear mixed-effects model will be used for multigroup longitudinal comparisons with fixed effects for group (SVR versus relapse), time, and group/time interaction. A significant group/time interaction would indicate that the 2 groups had different patterns over time. A class variable will be used for time to allow an arbitrary average time pattern within a group. In addition to fixed effects summarizing average group responses over time, the model will accommodate random, patient-specific deviations in intercept and time effects. Correlations will be assessed by nonparametric Spearman rank correlation. Spotfire S+ 8.2 (TIBCO), Prism 6.0 software (GraphPad), and SAS 9.3 (SAS Institute, Inc.) will be used for statistical analysis and data presentation using a p-value of 0.05 to indicate statistical significance.
 
Power/Sample Size:
 
This is a pilot, prospective clinical trial comparing the host immune response using ISG expression, including IP-10 levels, and HCV specific T-cell responses between a historical, non-transplant cohort of 25 patients from IRB approved studies previously conducted at the IHV and post-renal transplant (immunosuppressed) patients and its association with SVR 12. The study team will perform an interim data and safety evaluation for the efficacy, safety, and tolerability of grazoprevir and elbasvir therapy. Data analysis will focus on the clinical efficacy endpoint of SVR 12 with secondary analysis looking at the relationship of the host immune response markers with the primary endpoint of SVR 12 in both groups.
 
We anticipate enrollment of 25 patients in this arm of the study. This will be compared to a historical control group of 25 patients with stored blood samples from previous IRB approved clinical trials conducted at the IHV.
 
We anticipate a SVR 12 of greater than 90% in the grazoprevir plus elbasvir treatment group post-renal transplantation. With 50 participants (25 in this study and 25 historical controls), the study will be able to estimate the difference in SVR12 proportions to within ± 0.18 (Table 2). Table 2 shows a substantial gain in precision by increasing the sample size from 15 per arm to 25 per arm; however, the effect diminishes beyond 25.
 
Table 2: Sample Size Calculation for SVR12
 
  
 N per arm	15	20	25	30	50	
   
 Accuracy to within \pm	0.24	0.20	0.18	0.17	0.13	
  
	N per arm	15	20	25	30	50	Accuracy to within \pm	0.24	0.20	0.18	0.17	0.13

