N per arm	15	20	25	30	50								
Accuracy to within \pm	0.24	0.20	0.18	0.17	0.13								
2.8 Specific Drug Supply Requirements	
We request study drug supply from Merck Inc. for all study subjects. The study drugs will be received and distributed by [name], RPh, through the UMD investigational drug pharmacy. The study drugs will be stored under the conditions specified by the manufacturer. Packaging and labeling will be done by Merck. At the study's conclusion the remaining investigational product will be disposed of according to the ICH/GCP guidelines and our institution's policies.
												
2.9 Adverse Experience Reporting	
2.9.1 Overview
 
Adverse experience reporting will be performed per study agreement at each study visit. During each clinical evaluation with the patients, information regarding adverse events and adverse reactions will be elicited. Any untoward or unfavorable medical occurrences will be recorded, whether or not considered related to the patient's participation in the research. Additionally, patients may be seen at unscheduled visits for a grade 3 or 4 adverse event or any unexpected adverse event or potential toxicity.
												

Adverse events (AEs) classified as serious or grade 3 or higher will be reported to the principal investigator. Any grade 3 or 4 AEs and all SAEs will be reviewed as they occur by the study team. Any AEs found to be occurring above the level expected by the study team will be reported to the IRB and study sponsor.

For this study, patients may have expected AEs related to transplantation in the post-transplantation arm or related to renal failure in the pre-transplantation arm. This protocol will record all AEs possibly related to the treatment of HCV as defined by the Office for Human Research Protections (OHRP) (21).

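### The safety endpoint counts severe adverse events, its only reference rate is for serious ones, and the one-sample test against historical controls has no stated null

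*Combined protocol and SAP*

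**What the plan says.** Section 2.7, Secondary Objective 1, defines the safety endpoint: "The primary endpoint for this objective will be the presence of any severe adverse event". Shortly afterwards, citing the published trial in chronic kidney disease, it gives an expected rate: "we estimate rate of serious adverse events of about 15" per cent. Statistical Methods in the same section goes back to the first term and bases the analysis on the "proportion of patients with SVR 12 and severe adverse events, respectively, with point estimates and 95% confidence interval".

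The protocol separates the two terms. Section 2.9.2 defines a serious event by its outcome (death, threat to life, hospitalization, disability and so on). Section 2.9.3.1 uses the word severe for CTCAE grade 3. Section 2.9.1 lists both classes side by side: "Adverse events (AEs) classified as serious or grade 3 or higher will be reported to the principal investigator".

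The comparison is specified in one sentence for both endpoints: "Both primary efficacy and safety endpoints will be compared to a non-transplant, HCV-infected historical control group by using two-sided, exact one-sample binomial test", at the 0.05 level. No null proportion is given. Two sources could supply one:

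- **The 15%.** It comes from a trial that section 2.2 describes as follows: "The study participants were HCV genotype 1, CKD stages 4/5 (eGFR <30), and 76% were on hemodialysis".
- **The institution's own controls.** Section 2.7, Power/Sample Size, describes a "historical control group of 25 patients with stored blood samples from previous IRB approved clinical trials", and section 2.2 calls them "a cohort of historical, non-transplant patients treated for HCV in whom we have stored blood samples from prior IRB-approved studies". No adverse event rate is given for them.

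Secondary Hypothesis 1 (2.1.1) predicts no significant difference in safety from non-transplant patients and gives no margin.

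**The concern.** There are two separate faults.

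**Event class.** Followed literally, the plan counts severe events and offers a benchmark for serious events. A severe event need not be serious, and the reverse also holds, so the two rates can differ in either direction. An apparent excess or deficit could come from the definition alone.

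**Null and test.** A one-sample binomial test needs a fixed proportion. Without one, the count that would be declared significant is undetermined until someone chooses a null, possibly after the data are seen. If the null is the rate observed in 25 controls, the test ignores the sampling error in those controls and no longer holds its nominal 5% level.

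The wording of Secondary Hypothesis 1 adds a third risk: a non-significant result in 25 patients could be reported as evidence of similar safety.

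**Working it through.** **Inputs from the plan.** 25 treated patients; 25 historical controls; two-sided exact one-sample binomial test at 0.05; about 15% expected serious events. The 15% is a cited figure, so it cannot be reproduced from the documents. Section 2.7 gives no power or precision for safety; Table 2 covers SVR12 only.

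**Assumptions.** All true event rates below, and all nulls other than 15%, are assumed. Using 15% as the null is itself an inference. The plan does not name the version of the exact test, so two are shown: minimum-likelihood first, equal-tail second.

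**1. How far the missing null matters.** For X ~ Binomial(25, p0), the test rejects where the two-sided exact p ≤ 0.05.

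| Assumed null p0 | Smallest count significant as an excess (min-likelihood / equal-tail) |
|---|---|
| 10% | 6 / 7 |
| 15% | 8 / 9 |
| 20% | 10 / 10 |

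At p0 = 15% the only count significant as a deficit is 0. Actual size is 4.3% / 2.5%. The same result, 8/25, gives p = 0.002, 0.043 or 0.14 (minimum-likelihood) at nulls of 10%, 15% or 20%.

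**2. Reading A: 15% is the null, but severe events are counted.** The chance of a false excess is P(X ≥ 8) or P(X ≥ 9) at the true severe-event rate. The chance of a false deficit is P(X = 0) = (1 − p)^25.

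| True severe-event rate (assumed) | False excess (min-likelihood / equal-tail) | False deficit |
|---|---|---|
| 30% | 49% / 32% | – |
| 25% | 27% / 15% | – |
| 20% | 11% / 5% | – |
| 10% | – | 0.90^25 = 7% |
| 5% | – | 0.95^25 = 28% |

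**3. Reading B: the null is the rate observed in the 25 controls.** Let c be the control count and set p0 = c/25. With the same true rate p in both groups,

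type I error = Σ over c of P(c) × P(X falls in the rejection region for p0 = c/25).

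Here 0/25 controls gives a null of 0, so any treated event rejects.

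| True rate in both groups (assumed) | Type I error (min-likelihood / equal-tail) | Contribution of 0/25 controls removed |
|---|---|---|
| 10% | 18.2% / 15.2% | 11.5% / 8.5% |
| 15% | 18.1% / 13.9% | 16.4% / 12.2% |
| 20% | 17.8% / 13.9% | 17.4% / 13.5% |
| 30% | 17.4% / 13.0% | 17.4% / 13.0% |

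**4. Two-sample tests in the same setting (25 v 25).**

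| | Fisher | Boschloo |
|---|---|---|
| Type I error at 15% v 15% | 1.9% | 3.1% |
| Power at 30% v 15% | 15% | 22% |
| Treated events needed against 4/25 controls | 12 | 11 |

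Boschloo here uses the two-sided Fisher p as its statistic, with critical value 0.079 and maximum size 4.6%. Against the same 4/25 controls, the one-sample test would call 8 (equal-tail 9) treated events significant; for 8/25 v 4/25, Fisher gives p = 0.32.

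**5. What 25 patients can show.** 4/25 = 16%, exact (Clopper-Pearson) 95% CI 4.5% to 36.1%. For 4/25 v 4/25 the difference is 0, with Newcombe 95% CI −21 to +21 percentage points.

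**The case against.** The strongest reply has five parts.

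- **The two harms are alternatives.** Step 2 needs 15% to be the null; step 3 needs the controls to be the null. This is right, and the figures must not be added together. The plan does not say which reading applies, and each reading has a fault.
- **The comparator is not really open.** The text points to the 25 institutional controls, and the 15% is only a planning expectation. That is the more natural reading. It makes step 3 the relevant calculation, and there the stated test fails to hold its level.
- **Severe may be a slip for serious.** Possibly. But the word stands in both operative sentences, the protocol defines both terms, and correcting it would still leave the null unstated.
- **The inflation depends on how 0/25 controls is handled.** In part. Without that outcome, type I error falls to 11.5% at a true rate of 10% (equal-tail 8.5%), which is still above 5%.
- **The consequence is limited.** This is a secondary objective in an open-label pilot, an estimate with a 95% CI is already planned, and safety oversight (event-by-event review and the DSMB, sections 2.9.1 and 2.9.6) does not depend on the test. All of this stands and limits the weight of the point.

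It is also fair that the controls are described by stored blood, not by safety records, and that no two-sample test removes the bias of a non-randomized comparison. But the plan already commits to a safety comparison with a historical group.

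**Conclusion.** The concern holds and should be fixed. The endpoint and its only reference rate belong to different event classes, and the test lacks the fixed proportion it needs. On the more natural reading, with the 25 controls as comparator, the false-positive rate is about 18% (equal-tail 14%) at assumed true rates of 15%, roughly three times the stated 5%. On the other reading, with 15% as the null, a false excess would appear in 11% to 49% of trials for assumed true severe-event rates of 20% to 30% (equal-tail 5% to 32%), and a false deficit in 7% or 28% at 10% or 5%. These percentages illustrate the effect, because the documents give no severe-event rate. The textual mismatch and the missing null do not depend on them. The planned point estimate and its interval remain usable once the event class is settled.

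**What to change.** 1. **One event class.** In section 2.7, use the same term in the endpoint definition and in Statistical Methods: either serious as defined in 2.9.2, if the 15% is kept, or grade 3 or higher as graded in 2.9.3.1, with a matching sourced rate.
2. **One comparator.**
   - If it is a published rate, state it as the fixed null with its source, count events by that source's definition, attribution and observation window, and name the version of the exact test.
   - If it is the 25 historical controls, replace the one-sample test with a pre-named two-sample exact test (Fisher or Boschloo, for example) and a 95% CI for the difference, with the same event class, attribution and window in both groups.
3. **Conclusion.** Rest the safety statement on the estimate and its 95% CI, and reword Secondary Hypothesis 1 (2.1.1) so that p>0.05 is not read as similar safety.

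**Cost.** Wording in 2.1.1 and 2.7, plus one sourced rate or a tabulation of control events; no new visits or data in the trial arm. The tabulation depends on comparable adverse event records existing for the controls, which the plan does not describe. The safety statement becomes visibly less precise, as step 5 shows. Power also falls: for 30% v 15% (assumed), Fisher has 15% and Boschloo 22%, against 49% (equal-tail 32%) for a one-sample test with a fixed 15% null. If grade 3 or higher is chosen, the 15% can no longer be used.

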2.1 Objectives & Hypotheses	<h3>2.1 Objectives and Aims</h3> 
Aims
 
1. To evaluate the determinants of Sustained Virologic Response (SVR) in patients treated with grazoprevir and elbasvir in the presence of immunosuppression (post-renal transplant). 
Primary Objective
 
1. To determine the difference in the host immune response as measured by interferon stimulated gene (ISG) expression (IP-10 in particular), and HCV specific T-cell response in post-renal transplant patients compared to historical, non-transplant patients and its association with SVR.2. To examine the efficacy of grazoprevir and elbasvir in patients post- renal transplantation compared to historical, non-transplant patients. 
Secondary Objectives
 
1. To evaluate the safety and adverse events of grazoprevir and elbasvir post-renal transplant patients compared to historical, non-transplant patients.2. To describe the effects of chronic HCV treatment on two-year renal allograft outcomes in patients treated after renal transplantation. <h4>2.1.1 Clinical hypotheses</h4> 
Primary Hypotheses
 
1. Patients treated for chronic HCV with grazoprevir and elbasvir after renal transplantation will maintain a robust host immune response as measured by ISG expression (IP-10 in particular) and HCV specific T cell responses in the presence of immunosuppression.2. The proportion of patients who achieve SVR12 will be greater than 90% in post-renal transplant patients. 
Secondary Hypotheses
 
1. The safety, tolerability, and adverse events of treatment with grazoprevir and elbasvir in patients with chronic kidney disease will not be significantly different in post-transplant patients compared to non-transplant patients.2. The treatment of chronic HCV using grazoprevir and elbasvir will improve the renal allograft outcomes in terms of rejection or graft survival. <h4>2.1.2 Clinical Impact</h4> 
Chronic HCV in patients with CKD is associated with an increased risk of death as well as renal transplant graft failures (1). With the FDA approval of grazoprevir and elbasvir, we now have a regimen that can be used in these patients with severe CKD. However, it remains unknown if there is an immunologic advantage for both achievement of SVR 12 and renal allograft outcomes in treating these patients prior to their transplant compared to waiting until after transplantation when they will be immunosuppressed. And while we predict that transplant recipients will maintain high rates of SVR, it is uncertain whether these immunosuppressed transplant recipients will maintain robust host immune responses to HCV treatment.

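### SVR12 and severe adverse events are tested against a 25-patient historical group by a one-sample binomial test that has no stated null rate and ignores the controls' sampling error

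*Combined protocol and SAP*

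**What the plan says.** Under Statistical Methods in section 2.7, the efficacy and safety analyses are "based on the proportion of patients with SVR 12 and severe adverse events, respectively, with point estimates and 95% confidence interval". Both endpoints are then to be "compared to a non-transplant, HCV-infected historical control group by using two-sided, exact one-sample binomial test at a significance level of 0.05". No null proportion is given, and nothing says how one would be derived from the control group.

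The Power/Sample Size part of section 2.7 describes the comparator as a sample: "This will be compared to a historical control group of 25 patients with stored blood samples". It bases precision on 50 participants, 25 in each group, and states that "the study will be able to estimate the difference in SVR12 proportions" to within ±0.18. Table 2 gives half-widths of 0.24, 0.20, 0.18, 0.17 and 0.13 for 15, 20, 25, 30 and 50 per arm.

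Other rates appear in the document, but none is named as the null:

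- Section 2.1.1 hypothesises that "The proportion of patients who achieve SVR12 will be greater than 90% in post-renal transplant patients".
- Section 2.2 cites a trial in CKD stages 4/5 with "intention to treat (ITT) and modified ITT analysis of 94% and 99% for SVR12".
- Section 2.7, Secondary Objective 1, says "we estimate rate of serious adverse events of about 15" per cent.

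**The concern.** This is the only test specified for Primary Objective 2, the efficacy comparison with non-transplant patients. A one-sample test treats the comparison rate as known. A rate observed in 25 patients is not known; it carries as much sampling error as the rate in the transplant arm. The sizing recognises this and the test does not. The Statistical Methods text also gives no method for the difference that Table 2 plans to estimate.

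The wording can be read in two ways, and each leaves a problem. If the observed control rate is the null, the test does not hold 5%, and most of the excess points to transplant patients doing worse. That bears directly on the question in sections 2.1.2 and 2.2 of whether to treat before or after transplantation. If a fixed benchmark is the null, it remains to be chosen at analysis, when the data can be seen.

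For safety, the 15% estimate does not fill the gap. It refers to serious events, while the tested endpoint is severe events; sections 2.9.2 and 2.9.3.1 define the two differently.

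**Working it through.** **Inputs.** 25 transplant patients, 25 historical controls, two-sided 0.05 and the Table 2 half-widths, all from section 2.7. SVR12 rates of 90% (section 2.1.1) and 94% and 99% (section 2.2). The 15% event rate from section 2.7, used for illustration only. True rates of 85% and 97% are added to show the range.

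**1. Reproducing Table 2.** The two-sample Wald half-width is 1.96 × √{[p1(1−p1) + p2(1−p2)]/n}. With p1 = 0.90 and p2 = 0.85 the bracket is 0.09 + 0.1275 = 0.2175, which gives:

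| n per arm | 15 | 20 | 25 | 30 | 50 |
|---|---|---|---|---|---|
| Computed | 0.236 | 0.204 | 0.183 | 0.167 | 0.129 |
| Table 2 | 0.24 | 0.20 | 0.18 | 0.17 | 0.13 |

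All five entries match. The 90%/85% pair is back-calculated, not stated, and other pairs fit too (for example 87.5%/87.5%). A one-sample half-width at 90% is 1.96 × √(0.09/25) = 0.118, so Table 2 is not a one-sample calculation at the anticipated rate.

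**2. Null set to the observed control rate.** For control count c and transplant count x, each from 0 to 25, take the exact binomial p-value of x with null c/25. The error rate is the sum of Bin(x; 25, π) × Bin(c; 25, π) over all pairs with p ≤ 0.05, where π is the common true rate. Two-sided exact p-values have two common conventions, shown as minimum-likelihood / doubled smaller tail. With c = 25 the null is 100% and a single failure rejects, so the sum is repeated with that case (c = 0 for adverse events) counted as no rejection.

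| Common true rate | All outcomes | Degenerate control result not tested |
|---|---|---|
| SVR12 85% | 18.1% / 13.9% | 16.4% / 12.2% |
| SVR12 90% | 18.2% / 15.2% | 11.5% / 8.5% |
| SVR12 94% | 21.0% / 20.3% | 4.2% / 3.5% |
| SVR12 97% | 25.4% / 25.4% | 0.6% / 0.5% |
| Adverse events 15% | 18.1% / 13.9% | 16.4% / 12.2% |

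At 90%, the part that falls as transplant worse is 14.2 of 18.2 points (12.5 of 15.2 doubled-tail). Without the 25/25 case it is 7.6 of 11.5 (5.8 of 8.5). Fisher's two-sample test rejects at most 2.2% of the time for true rates from 80% to 99%.

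**3. An ordinary data set.** Controls 23/25, transplant 19/25. The one-sample test against 0.92 gives p = 0.012 / 0.025. Fisher's test gives p = 0.25. The difference is −16 points, with a Newcombe 95% interval from −36 to +5.

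**4. Null set to a fixed benchmark.** The actual level is 3.3% / 0.9% at 90%, 1.5% / 1.5% at 94% and 2.6% / 0.2% at 99%, so the test is valid. The choice still matters:

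| Result | Benchmark | p | Benchmark | p |
|---|---|---|---|---|
| 20/25 | 90% | 0.098 / 0.20 | 94% | 0.015 / 0.030 |
| 22/25 | 94% | 0.19 / 0.37 | 99% | 0.002 / 0.004 |

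Against 90%, even 25/25 gives p = 0.17 / 0.14.

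**The case against.** The strongest reply is that a one-sample exact test normally goes with a fixed historical benchmark, and such a test holds its level. On that reading all the inflated error rates fall away and only an unnamed null remains. This is fair: the plan never says that the observed control rate becomes the null, and the figures in step 2 depend on that reading. But the plan says the comparison is with a control group, and it describes that group as 25 patients. A benchmark reading would still have to say which benchmark.

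Second, the degenerate 25/25 control result drives much of the inflation. At a true 94% or more this is largely right, and without that case the error there is below 5%. At 85% and 90% a clear excess remains, and the direction is still mostly transplant worse.

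Third, the starkest benchmark contrast uses the 99% modified-ITT figure, although the plan labels its own analysis intention-to-treat. Between 90% and 94% the verdict changes only at 20/25 by minimum likelihood, or at 19/25 and 20/25 by doubled tail. That limits how often the choice matters but does not remove it.

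Fourth, Table 2 covers SVR12 only, so tying the 25 controls to the safety test is an inference. The inference is reasonable, because one sentence sends both endpoints to the same control group.

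Finally, this is a pilot sized on precision, and the plan already promises point estimates with intervals. Those are for the transplant proportions, however, and a formal test at 0.05 is still specified.

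**Conclusion.** The concern holds. The plan names a test without its null, and that test does not match the two-sample SVR12 comparison on which the study is sized. This should be fixed before analysis.

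The size depends on the reading. With the observed control rate as null and a common true SVR12 of 85% to 90%, the nominal 5% test rejects about 14% to 18% of the time, or 8.5% to 16.4% if a 25/25 control result is not tested. At 94% and above, the excess comes from that degenerate case. With a fixed benchmark the error rate is controlled, but the conclusion can depend on a choice the plan leaves open.

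The calculations treat both groups as independent binomial samples of 25. They do not address how the historical controls were selected, which may bias the comparison whichever test is used.

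**What to change.** In section 2.7, Statistical Methods, replace the one-sample test for both endpoints with a two-sample comparison against the 25 historical controls. Report the difference in proportions with a Newcombe or exact unconditional 95% confidence interval and, if a p-value is wanted, Fisher's or Barnard's exact test. State the control rate behind ±0.18. The analysis would then estimate the quantity in Table 2.

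If a fixed benchmark is really intended, prespecify and justify one null rate per endpoint, with the safety rate defined for severe events. State the exact p-value convention, and describe the result as a comparison with that benchmark and not with the 25-patient group.

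The two-sample option is a wording change, but it needs SVR12 and severe-event outcomes for the same 25 controls. Significant p-values will be rarer: with controls at 25/25, Fisher's test needs 19/25 or fewer in the transplant arm (p = 0.022), since 20/25 gives 0.0502. The benchmark option has its own limit: against 90% no result, not even 25/25, could confirm the hypothesis that SVR12 exceeds 90%.
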